**Measures of comorbid anxiety, depression, and alcohol abuse** will include the *Structured Clinical Interview for DSM-IV* (SCID, Spitzer, et al. 1994), the *[name] Anxiety Inventory*, the *[name] Depression Inventory – II*, and an amended version of the *Short Inventory of Problems*. The SCID has been discussed in Section D1 (Study Participants). Both measures derived from the SCID (presence/absence of each additional disorder and global Clinical Severity Rating for each disorder) will be used. The SCID will not be administered at mid-treatment assessment. Other measures are:

- The [name] Anxiety Inventory (BAI; [name] et al., 1988) will be administered as a continuous measure of anxiety. The BAI is a 21-item scale that assesses anxiety and is believed to avoid confounding anxiety with depression. The BAI has established psychometric properties ([name] & Steer, 1991).
- The [name] Depression Inventory-II (BDI-II; [name] et al., 1996) will be administered as a continuous measure of depression. This 21-item questionnaire evaluates current depressive symptoms and has well-established reliability and validity ([name] et al., 1996).
- An amended version of the Drinkers Inventory of Consequences, named the Short Index of Problems (SIP; Miller et al., 1995) will be used to assess alcohol use and alcohol-related consequences. The SIP is a 15-item scale that includes five subscales: physical consequences, intrapersonal consequences, social responsibility consequences, interpersonal consequences, and impulse control consequences. The SIP possesses satisfactory psychometric properties (i.e., good internal consistency, good concurrent validity, good test retest reliability; (Forcehimes et al., 2007). The SIP will be supplemented with three questions that will assess how many days in the past 2 weeks the individual consumed alcohol, on average how many standard drinks were consumed on those days when he drank alcohol, and the number of days in the past 2 weeks on which 5 or more standard drinks were consumed. This assessment strategy was constructed in consultation with [name], Research Institute for the Addictions, Buffalo, NY. We have included a mid-treatment assessment period in our design; however, in order to reduce participant-burden we will not conduct the SCID diagnostic interview at the mid-treatment assessment time period.

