In any RCT, missing data are inevitable. Analysis of only complete cases is biased; likewise, values not missing at random can bias the results. Thus, analyses that impute missing data must accordingly increase standard errors. In designing this trial, we have included features that are intended to minimize attrition, such as the presence of a project coordinator (who will make regular contact with each patient before and after treatment). Even with these features, we expect some missing data. The analytic plan is designed to make maximum use of the data. In particular, we will use multilevel latent growth modeling (estimator = maximum likelihood [ML]) using Mplus software. Within this approach, missing data are handled with direct ML (cf. Allison, 2001), retaining an effective  $N = 196$  for all analyses. In addition to fostering statistical power, modern missing data methods such as direct ML (and multiple imputation) provide accurate parameter estimates and standard errors (assuming that values are missing at random), unlike traditional methods such as restricting analyses to completers only or intent-to-treat (ITT) analyses. If we suspect that values are not missing at random, we will turn to methods discussed by Molenberghs and Kenward (2007), that are likelihood-based, intended for ITT studies, and tractable enough for standard statistical programs such as SAS. Potential bias due to attrition will be assessed by modeling 'missingness' patterns. In effect, these methods increase standard errors of the crucial study estimates thereby accounting for this source of uncertainty. If attrition occurs in a random manner (missing at random implies 'missingness' may depend on covariates but not on previous values of the outcome measure) then the mixed model produces unbiased estimates and conservative standard errors. Evaluations of potential bias, when attrition is not missing-at-random, requires cutting-edge statistical methodology (Daniels & Hogan, 2008). We will perform sensitivity analysis under various not-missing-at random assumptions following Daniels and Hogan's (2008) methodology.

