extent of dependency (i.e., clustering) by calculation of intraclass correlations (ICCs) using variance estimates from unconditional cell means models of key outcome variables (cluster = treatment group). Our proposed  $N$  of 196 will be clustered into 14 treatment groups per condition. Assuming non-zero ICCs, a multilevel approach will be incorporated into the latent growth framework in order to obtain correct standard errors, test statistics, and confidence intervals. In the traditional multilevel modeling, the design would be construed as a three-level model; i.e., repeated observations (Level 1) nested under individuals (Level 2), individuals nested under treatment groups (Level 3). However, because the first two levels are combined in the multivariate framework of latent growth modeling, this design can be characterized as a two-level model (i.e., latent growth factors are nested under treatment groups) where time-invariant covariates (i.e., dummy codes for treatment condition) are included to account for the within-group and between-group variability in initial status (pre-treatment) and symptom change (improvement over active treatment and follow-up). In the latent growth model portion of the models, the intercept will be centered on pre-treatment (i.e., first slope loading will be fixed to 0.0). Because there is no substantive interest in the form of the growth trajectory, intermittent time points (i.e., slope factor loadings) will be freely estimated and the final timepoint of interest (e.g., post-treatment) will have a corresponding factor loading fixed to 1.0. Accordingly, the mean and variance of the slope will convey the fixed (average) and random effects (individual differences) of change for the given time interval of interest. The Level 2 variables of treatment condition (single dummy code using *SGP* as reference group) will be included as predictors to account for individual differences in treatment response and variability in outcome across treatment groups. To examine pre-treatment differences between treatment conditions, the intercept (centered on pre-treatment) will be regressed onto the treatment covariates (i.e., significant paths are indicative of differences in pre-treatment levels as a function of treatment condition). Any pre-treatment differences will be accommodated into the interpretation of findings and in the parameterization of the models (e.g., regression of the slope onto the intercept, as well as covariates such as treatment condition). The dependent variable for this analysis is the CAPS total score. Additionally, PCL will be examined, using the same analytic approach, in order to examine respondent effects (interviewer-rated versus self-report).

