
***Hypothesis 2.*** Reductions in PTSD symptom severity will be maintained in the GCBT group at 12-month follow-up. Much as with Hypothesis 1, multilevel latent growth modeling will be used. In the analyses to examine Hypothesis 2, we will not include the treatment condition covariate but will include the site dummy code, to examine potential site differences. To test the prediction that the means of 6mos and 12mos do not differ, the slope factor loadings corresponding to these two time points will be constrained to equality and compared to the fit of a latent growth model where the 6 mo time point was freely estimated ( e.g., Baseline model:  $0^{* * 1}$ ; hypothesized model:  $0^{* * 1} 1$ ).

The **secondary aim** is to examine the generalizing effects of both GCBT and *SGP* on co-morbid conditions, distress and impairment. Because most trials in the PTSD literature do not include a thorough assessment of treatment generalization, it is unknown whether available treatments only address PTSD or whether gains generalize to related domains of functioning, including co-

morbid conditions such as depression, generalized anxiety, and alcohol use. Three hypotheses are proposed:

**Hypothesis 3.** For patients who are diagnosed with co-morbid Major Depressive Disorder (MDD), Generalized Anxiety Disorder (GAD), and/or Alcohol abuse prior to treatment, GCBT will produce significantly larger symptom reductions for these conditions, relative to SGP at post-treatment assessment and these generalized changes will show stability at 6 mo follow-up (FU). To test this hypothesis, we will use multi-level analysis, as discussed for Hypothesis 1. For continuous variables (BAI, BDI-II, SIP), we will use the same approach as described for Hypothesis 1. Although latent growth modeling can accommodate categorical outcomes (e.g., MDD+, MDD-) with an appropriate estimator (e.g., robust weighted least squares, maximum likelihood with numerical integration), there is concern about the estimation failure resulting from low cell frequencies, particularly at post-treatment and follow-up. In the event that cell frequencies are too low, we will augment the analyses from the continuous variables with more descriptively oriented statistics showing the rates of comorbidity decline at each assessment point as a function of treatment condition.

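### If each comorbid diagnosis is analysed in the men who had it before treatment, the optional categorical growth model for Hypothesis 3 has a constant baseline indicator; comparing post-baseline diagnosis by arm avoids this

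*Combined protocol and SAP*

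**What the plan says.** Hypothesis 3 (Section D.7.a) concerns a selected set: "For patients who are diagnosed with co-morbid Major Depressive Disorder (MDD), Generalized Anxiety Disorder (GAD), and/or Alcohol abuse prior to treatment". Its prediction is that "GCBT will produce significantly larger symptom reductions for these conditions". The committed test uses the continuous scales (BAI, BDI-II, SIP), analysed as for Hypothesis 1.

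For diagnoses, the same paragraph says only that latent growth modelling can handle a categorical outcome with a suitable estimator, giving as examples "robust weighted least squares, maximum likelihood with numerical integration". It then warns that "there is concern about the estimation failure resulting from low cell frequencies, particularly at post-treatment and follow-up". If cells prove too sparse, the continuous analyses are to be supplemented by descriptive rates of comorbidity at each assessment, by condition.

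Three other places bear on this:

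- Section D.7.a, Hypothesis 1: "the intercept will be centered on pre-treatment", with the first slope loading set to zero. The intercept is regressed on condition, and the slope mean is to be read as average change.
- Section D.4, comorbidity measures: both SCID measures are to be used, namely "presence/absence of each additional disorder and global Clinical Severity Rating for each disorder". Also, "The SCID will not be administered at mid-treatment assessment".
- Analytic approach, missing-data paragraph: multilevel latent growth modelling with "estimator = maximum likelihood [ML]) using Mplus software", and missing values handled by direct maximum likelihood. Missing at random is defined there as missingness that may depend on covariates but not on earlier outcomes.

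**The concern.** Selecting men because they have a diagnosis and then using that diagnosis as the first indicator of a growth model makes the indicator constant. The plan expects sparse cells mainly after baseline. On the per-diagnosis reading the one cell certain to be empty is at baseline, and the text does not mention it.

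At stake is the interviewer-rated diagnosis outcome. SCID assessors are blinded to condition (Section D.1), whereas the BAI, BDI-II and SIP are completed by men who know which group they attend. The SCID severity rating is not among the continuous variables listed for Hypothesis 3. If the categorical model breaks down and the fallback applies, the blinded comorbidity data get descriptive rates by arm but no specified estimate, interval or test.

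A second, smaller issue is that weighted least squares works from available-case thresholds and correlations. It is therefore not the direct maximum likelihood that the plan describes, and it tolerates fewer kinds of dropout.

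**Working it through.** The plan gives no figure for this analysis, so there is none to reproduce. The overall sample size does not bear on the point.

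**Step 1. Occasions.** The SCID is skipped at mid-treatment, so the diagnosis series to 6 months is pre-treatment, post-treatment, 3 and 6 months. For a model ending at post-treatment, only pre and post remain.

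**Step 2. Baseline indicator, one set per diagnosis.** The share positive is p = 1. Its variance is p(1 - p) = 1 x 0 = 0. The probit threshold has magnitude |Φ⁻¹(1)|, which is infinite. Weighted least squares therefore has no usable baseline threshold, and the correlations of baseline with later visits are undefined.

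**Step 3. Maximum likelihood, same set.** Simulated data, 150 men, all positive at baseline. Binary probit growth model with loadings 0 at pre-treatment, free at post and 3 months, and 1 at 6 months; numerical integration; one arm coefficient; group clustering left out. The intercept mean was fixed in turn and the other parameters maximised:

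| Intercept mean | Log-likelihood | Slope mean | Arm coefficient | Free loadings |
|---|---|---|---|---|
| 2 | -293.04 | -2.45 | -0.090 | 0.78, 0.86 |
| 3 | -289.79 | -3.44 | -0.083 | 0.84, 0.91 |
| 4 | -289.60 | -4.44 | -0.079 | 0.88, 0.93 |
| 6 | -289.61 | -6.43 | -0.076 | 0.92, 0.95 |
| 8 | -289.63 | -8.43 | -0.075 | 0.94, 0.96 |
| 12 | -289.64 | -12.43 | -0.073 | 0.96, 0.98 |

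From 4 to 12 the log-likelihood changes by 0.04. The data say the intercept is high but not how high, and the slope mean offsets it almost one for one. Neither is identified, so the slope mean cannot be read as average change. The arm coefficient stays between -0.083 and -0.073 from 3 upward. This shows that the post-baseline contrast is estimable; it does not test its accuracy. The plan's further path, intercept on condition, has no baseline variation to rest on.

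**Step 4. Pooled reading.** Simulated data, 200 men, assumed baseline share 0.75. The log-likelihood is -472.8, -468.1 and -476.0 at intercept means 0.5, 1 and 1.5. There is a clear maximum, and the model can be fitted.

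**Step 5. Dropout and weighted least squares.** Simulated two-visit probit, true arm effect -0.50 at the second visit, assumed dropout. The available-case probit is the first step of weighted least squares.

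| Dropout depends on | Available-case probit | Joint ML |
|---|---|---|
| Arm only (30% v 10%) | -0.497 | -0.503 |
| Earlier diagnosis, same in both arms (40% v 10%) | -0.495 | -0.499 |
| Earlier diagnosis, GCBT only (45% v 10%) | -0.639 | -0.497 |

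In the second row the arm effect survives but the control-arm level does not: 0.174 against a true 0.30 (joint ML 0.298).

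On the rate scale, for one arm, assume half the men are still diagnosed at post-treatment, with 80% of them and 20% of the remitted diagnosed at 6 months. The true rate is 0.5 x 0.8 + 0.5 x 0.2 = 0.50. If 10% of remitted men and a share d of the others leave, the observed rate is [0.5(1 - d) x 0.8 + 0.5 x 0.9 x 0.2] / [0.5(1 - d) + 0.5 x 0.9]. For d = 0.27, 0.35 and 0.50 this gives 0.469, 0.452 and 0.414, or 3 to 9 points low. None of these inputs is in the documents.

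**The case against.** The strongest reply is that the plan does not commit to this model. It mentions it in a concession, doubts it at once, and rests Hypothesis 3 on continuous scales that measure symptom reduction directly. That stands, and it limits the consequence.

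A reader might infer more than the documents support, in four ways:

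- **That every man certainly has the diagnosis at baseline.** The and/or wording also allows one pooled set, where each diagnosis varies at baseline and Step 4 shows the model fits. The plan's claim of an effective N of 196 for all analyses also sits awkwardly with diagnosis-specific subsets. Against pooling, men without a disorder at baseline cannot remit from it, which fits poorly with reductions in these conditions.
- **That the model cannot work at all.** Under maximum likelihood, which the plan also lists, the post-baseline arm contrast survives.
- **That weighted least squares is invalid under the plan's own missing-at-random assumption.** That assumption is covariate-only, and under it the method is consistent provided those covariates are in the model (first row of Step 5).
- **That the arm comparison is known to be biased.** Bias in the arm effect needs outcome-dependent dropout that differs by arm, and nothing in the documents shows this. The plan also intends to assess men who leave treatment and to run not-missing-at-random sensitivity analyses.

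The fallback does present rates by arm; what it lacks is a formal comparison.

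**Conclusion.** The concern holds in a limited form. On the per-diagnosis reading, the baseline indicator is constant by selection, weighted least squares has no baseline threshold, and maximum likelihood leaves the intercept and slope mean unidentified. The plan's warning about sparse cells does not mention this. If the fallback is then used, a blinded outcome that Section D.4 says will be used has no formal arm comparison.

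The identification result follows from the constant indicator; the simulated figures only illustrate it. The dropout figures show direction, and the size of any bias in this trial cannot be taken from the documents. Weighted least squares is a departure from the described direct maximum likelihood with a stricter missing-data requirement, not a contradiction of the plan's stated assumption.

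This is a secondary, optional analysis, and the continuous scales still test Hypothesis 3. It is worth correcting because a better comparison is available from data already being collected.

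**What to change.** 1. State the analysis set per diagnosis: men with that diagnosis before treatment.
2. Drop the constant baseline indicator. Model SCID diagnosis at post-treatment, 3 and 6 months with a logistic mixed model containing condition, visit, condition-by-visit and the baseline Clinical Severity Rating, with random effects for man and treatment group, fitted by maximum likelihood with numerical integration. The rating runs from 0 to 8, so it can differ among men who all have the diagnosis.
3. Report the difference in remission between arms, with 95% confidence intervals, at post-treatment and 6 months. Keep the descriptive rates as a supplement.
4. Remove weighted least squares, or state that it requires missingness not to depend on earlier diagnosis given the covariates in the model.

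The cost is SAP wording and a standard model; no new data are needed. The downside is sparseness. The documents give no prevalence per diagnosis; at an assumed 30% to 70% of 196, a set would hold 59 to 137 men across 28 treatment groups. The random-effects structure may need simplifying, and the order of simplification should be written down in advance.

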## **E. Human Subjects Research**

### **E.1. Risks to the Participants**

a. Human subjects involvement and characteristics: The participant population is to be comprised of 196 male veterans who will be recruited on the basis of presence of a current PTSD diagnosis stemming from military-related trauma. These individuals will be recruited on a volunteer basis. As indicated in the Methods section, inclusion criteria are that participants have chronic PTSD, and that any psychotropic medications are stable. Participants will be required to meet psychotropic medication stabilization criteria for the periods preceding and overlapping

with the diagnostic assessment and treatment. Patients using anxiolytics and beta-blockers will be required to maintain the same dosage for at least 1 month. Patients on antidepressants (tricyclics, SSRIs, MAO inhibitors) will have to have maintained a stable dosage for at least 3 months. If a patient is in the process of stopping his medication when he requests to be in the study, the medication wash-out period (i.e., period since medication discontinuation) will be 1 month for all medications. With respect to involvement in other psychotherapy, we will ask participants to refrain from participating in any active PTSD treatments but other treatment engagement will be permitted.

Exclusion criteria include current suicide risk meriting crisis intervention. We recognize that numerous factors can adversely affect the validity of our data (e.g., neurocognitive deficits, difficulties stemming from using English as a second language, confabulation, extreme restlessness, irritability, threatening behavior, florid psychosis, sexually inappropriate behavior). Some of these dimensions will be formally assessed (e.g., mental status will be assessed using the MoCA, psychosis, current substance dependence, and current bipolar disorder will be assessed using the SCID). As well, we believe that there are other dimensions that might suggest that a participant would be inappropriate for this study (e.g., homicidal risk meriting crisis intervention, acute intoxication). It would be impractical for us to attempt to operationalize all of these dimensions. Instead, we propose to rely on the clinical judgment of the interviewer and the consensus of the research team to determine the validity of an assessment. If a participant is obviously unable to comprehend or conform to the study procedures, the interviewer will terminate the protocol. In less obvious cases where there are concerns about the validity of an assessment but the participant completes the protocol nonetheless, the research team will review the assessment recording and determine, through consensus judgment, if the case should be excluded from analysis. We will use statistical exclusion of outliers as a final level of protection against invalidity. Details about any such exclusion will be included in all final reports and study publications.

Only individuals who provide written informed consent may participate. A participant may withdraw his consent at any time and without prejudice. A clear and detailed explanation will precede all procedures. At the beginning of the first assessment session, participants will be fully informed that they may be asked to talk about very personal and distressing experiences for the assessment and if they are uncomfortable with this possibility, they should not continue in the study. Participants will also be informed that they are free to withdraw from the study at any time without any consequences. An in-depth debriefing will explain all procedures and answer any questions. The debriefing will be conducted at the conclusion of the follow-up session. Any participant withdrawing early from the study will be provided with a debriefing at the time of withdrawal.

#### Inclusion of Women and Minorities

This project will not include women for two reasons. First, the number of female veterans seeking treatment for PTSD in the VA is considerably smaller than male veterans (8% versus 92% for female and male veterans, respectively). Second, women veterans presenting for PTSD services are more likely to present with PTSD related to sexual trauma (Fontana & Rosenheck, 2002), while combat-related PTSD is very uncommon among women veterans. We considered

running mixed male-female groups but recognized that the nature of the trauma exposure would likely be very different for male and female participants, which would require substantial revision to the GCBT program that is being tested here. In addition, women veterans with PTSD are very unlikely to agree to enroll in group treatment that includes men, and the small number of women who present for PTSD treatment within the VA system would limit our ability to recruit sufficient number of women to run women only groups. Thus, for both scientific and clinical practice reasons, we are recruiting only males in the proposed study.

Minority representation is expected as shown on the targeted Enrollment Table. We expect a fairly racially diverse sample based on veterans presenting for PTSD treatment at the VA Boston and VA Providence sites and past enrollment with PTSD clinical trials conducted at these two sites.

